Theorists have conjectured that the impact of AUA on suicide risk may depend on alcohol expectancies and increased suicide-related attentional bias. However, for obvious ethical reasons²⁷, no experimental tests of this hypothesis exist. Addressing these challenges, the proposed experiment is an ethical and innovative test of these hypotheses; it examines a construct theorized to occur early in the trajectory towards suicidal behavior but which has not yet been examined in relation to AUA: suicide-related attentional bias.³ This experiment complements NIAAA's strategic goals in basic science and prevention research, as it examines targetable cognitive factors that may influence suicidal ideation—a significant comorbidity among individuals with alcohol use disorders. This study challenges the current paradigm in alcohol-related suicide research in two important ways. First, it represents the first known experimental test of the AAM as it applies to suicide-related attentional bias and would guide methodology and parameters for future related studies, including those with samples higher in dysregulated mood. Further, this would be the first known study of suicide-related expectancies, another frequently hypothesized but untested correlate of alcohol-related suicide risk. If our hypotheses are supported, it would provide empirical support for a larger-scale test of the AAM as is relates to suicide risk. Future laboratory tests could test whether decreasing the salience of negative mood reduces suicide-related attentional bias. If alcohol expectancies are associated with suicide-related attentional bias, future work could test interactive effects of alcohol expectancies with mood and AUA on this bias. Downstream clinical implications include targeting expectancies and negative mood among individuals who consume alcohol. Ultimately, these findings may inform future basic and applied research examining the effects of AUA on suicidal ideation and behavior.

[figure not shown]
Approach

Consistent with theoretical and empirical work regarding the effects of AUA on suicidal thoughts and behaviors, this pilot study will test the interactive effects of Figure 2. Summary of Research Approach

AUA, negative mood, and alcohol expectancies on suicide-related attentional bias. The proposed study will employ a 2x2, between subjects design (alcohol-placebo X negative mood-positive mood, baseline levels of expectancies). See Figure 2 for a summary of our approach.

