In support of H3, we found that alcohol use strengthens the association of depressive symptoms with suicidal ideation in cross-sectional, observational studies of clinical samples.^{8,29} In support of H4, we found that alcohol expectancies related to mood and disinhibition change the problem drinking-suicidal ideation relation.⁹ In suicide decedents, we found that blood alcohol concentrations positively correlated with suicide means of rapid and high lethality, suggesting that AUA could be seen as reducing fear.³⁰ Similarly, in my cross-sectional and daily diary work (F31), AUA positively correlated with fearlessness and perceived pain tolerance.^{11,23}

Study Participants

A sample of 160 community adults (50% female; 10 pre-pilot; 150 pilot, about 38 per condition) will be recruited from the greater Birmingham area using flyers posted on the UAB campus and on Craiglist.com and Facebook.com (See *Recruitment and Retention Strategy*). Our original target pilot sample size was 120; however, we plan to oversample by 25% to account for the potential that 25% of participants may fail the mood induction. Participants will be told they are volunteering for a study testing "The Effects of Alcohol and Mood on

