Attention." Documented in the Statistical Design and Power attachment, the sample size is a compromise between feasibility and precision of estimates, and provides reasonable confidence interval widths for effect estimates. Inclusion criteria: a) be between the ages of 21 and 65, b) have consumed an average of at least five or more (four or more for females) standard alcoholic drinks per occasion once over the past year, c) have self-administered a quantity of alcohol that is equal to or greater than the dose that will be administered in the lab on at least three occasions in the past year, and d) be able to read and write in English fluently. Exclusion criteria: a) active psychosis, suicidal ideation/intent, or mania; currently receiving psychiatric treatment; have received psychiatric treatment in past year or currently experiencing significant psychiatric distress, b) in treatment or recovery from drug or alcohol use disorders or abstaining from alcohol, c) any suicide attempt history, d) pregnant/breast-feeding or immediate plans to become pregnant, e) any chronic health problems or medications that would preclude the use of alcohol, f) (to minimize adverse reactions to alcohol or inappropriate alcohol dose) < 6 feet tall and over 230 lbs., or > 6 feet tall and over 250 lbs. or weighing 15% below one's ideal body weight, g) (to minimize discomfort during lengthy study procedures) smoking more than 15 cigarettes a day, h) orange allergies, i) color-blind or sight-impaired, and j) knowing someone who has participated in this study. Given this is the first study to test the effects of AUA on suicide-related attentional bias, our exclusion criteria are conservative to reduce adverse events related to increased distress.

Procedures

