Prior to analysis, Suicide Stroop scores will be evaluated for outliers. We will exclude: trials with incorrect responses, trials with response latencies ± 2 SD from each participant's mean response latency, participants with a mean response latency ± 2 SD from the overall sample's mean, participants whose error rate was +2 SD above the error rate for all participants. We will also examine the reliability, factor structure, and concurrent validity for the suicide-related alcohol expectancies measure (created for this study) prior to its use for Hypothesis 3. We will use exploratory factor analysis (with parallel analysis), Cronbach's alpha, and examine associations with AUDIT total scores and past suicidal ideation severity. Finally, we will confirm there were no pre-existing relevant differences in mood states between our mood and alcohol conditions by estimating measures of association (i.e., R²) between condition assignment and pre-manipulation sad, guilty, and joviality mood states.

Pre-Pilot tests: To finalize study procedures, for the 10 pre-pilot subjects, we will examine prevalence of mood induction effectiveness. If >50% fail the mood induction, we will replace it with another effective mood induction (imaginative film). We will also run frequencies to examine percentage of participants who are successfully deceived, expecting these percentages to be high (>90%). We will use these results to adjust the protocol in order to improve success of our mood manipulation and deception.

Specific Aim 1, Hypothesis 1a: To test the feasibility our experiment, we will first quantify the number of individuals who contact our lab about the study and the percentage who are eligible and participate. We will run descriptive statistics to quantify 1) prevalence of successful mood induction (expecting at least 75%), 2) distress ratings after the study session (expecting average ratings to be low), and 3) number of adverse events (expecting less than 1% of pilot subjects). **Objective 1b:** Using measures of effect size (i.e., Cohen's d, Cramer's V) and t-tests and Chi square analyses, we will examine sociodemographic differences (gender, age, race/ethnicity, income, and alcohol use history) in these feasibility factors.

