For this training grant, as a compromise between feasibility and precision of estimates, I propose to recruit 10 pre-pilot subjects and 150 subjects (approximately 38 per condition combination) over a 2.5-year period. Assuming that 25% of subjects may be excluded due to mood induction failure, we will have 30 subjects per condition. Rather than traditional significance testing, the goal of the project is to examine feasibility and tolerability of procedures and explore observed effect sizes. Inference will be conducted primarily by estimation of 68% confidence intervals to be used as reasonable ranges for observed effect sizes. Following the proposed analysis of Hypothesis 3, it can be shown using variance algebra that the standard error of the effect of alcohol intake on Stroop interference scores within each of the mood induction groups (positive or negative) is $SE_{Alco.Eff} = \sigma \sqrt{2/n}$, where σ is the standard deviation of the Stroop interference scores and *n* is the sample size per condition combination. Thus, the standard error of the differential effect of alcohol intake conditional on mood induction (i.e. the interaction term) is $SE_{Diff.Alco.Eff} = 2\sigma/\sqrt{n}$. With n = 30 and standardizing the Stroop interference scores (i.e. $\sigma = 1$) to express the confidence interval in terms of an effect size (Cohen's d), the half width of a 68% confidence interval for the standardized effect of alcohol intake within each of the mood induction groups is .26 and the half width of a 68% confidence interval for the standardized differential effect of alcohol intake conditional on mood induction is .36, which provide reasonable and tolerable uncertainty ranges.

For completeness, in terms of null hypothesis significance testing (not a primary goal of this study), at a significance level of .05 the sample size provides 80% power to detect a standardized effect of alcohol intake

within each of the mood induction groups of .72, and standardized differential effect of alcohol intake conditional on mood induction of 1.

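### Hypothesis 1a pools adverse events over all conditions as one expectation below 1%, which 150 subjects cannot confirm and which says little about the alcohol-negative mood cell (minor improvement)

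*SAP*

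**What the plan says.** The SAP, under Specific Aim 1, Hypothesis 1a, introduces three feasibility items with "We will run descriptive statistics to quantify": successful mood induction, post-session distress, and "3) number of adverse events (expecting less than 1% of pilot subjects". No interval, test or decision rule is attached to the third. The Protocol's Analytic plan (H1) lists the adverse-event count with no threshold.

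Objective 1b gives the only planned breakdown: "we will examine sociodemographic differences (gender, age, race/ethnicity, income, and alcohol use history) in these feasibility factors". Beverage and mood condition are not on that list.

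The design is a "2x2, between subjects design (alcohol-placebo X negative mood-positive mood, baseline levels of expectancies". Protocol, Study Participants, gives the sample as "10 pre-pilot; 150 pilot, about 38 per condition", and the SAP's power section agrees: "I propose to recruit 10 pre-pilot subjects and 150 subjects (approximately 38 per condition combination) over a 2.5-year period". Since both documents separate the 10 from the 150, a percentage of pilot subjects most naturally refers to the 150.

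The Protocol expects risk to differ by condition. Its discussion of alcohol expectancies says that drinking in a negative mood often raises distress. Post-Study Interview and Debriefing justifies the safety interview partly by the negative induction and the alcohol that only some participants receive. Study Participants adds that "our exclusion criteria are conservative to reduce adverse events related to increased distress".

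**The concern.** About half the pilot sample receives placebo and about half the positive induction. If distress or reactions to alcohol concentrate where the Protocol suggests, these participants dilute the pooled percentage. One affected person in the alcohol-negative mood cell is 1/38 = 2.6% of that cell but 1/150 = 0.67% of the pilot, which is inside the expectation.

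The figure also has no statement of precision, although the SAP plans intervals for its effect estimates. Hypothesis 1a is the feasibility result, and the Protocol (Innovation; Potential Problems) hopes to guide later work in people with more dysregulated mood or more distress. A bare statement that fewer than 1% were affected would tell the planners of such a study little about the combination of alcohol and negative mood.

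The wording also leaves the count open. It combines a number of events with a percentage of subjects and does not say whether the 10 pre-pilot subjects count.

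**Working it through.** **Inputs.** Pilot n = 150 and pre-pilot n = 10 (both documents). Four cells: 150/4 = 37.5, stated as about 38. Two alcohol cells: about 75. Expectation: below 1% (SAP, Hypothesis 1a). Confidence level for effect sizes: 68% (SAP, Power and Sample Size Considerations). The true adverse-event risk by cell is not given, so the risks in step 4 are assumptions.

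**1. The plan's own figure.** The 1% has no derivation and cannot be reproduced. As a count: 1/150 = 0.67% meets it and 2/150 = 1.33% does not. It therefore means 0 or 1 affected participants.

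The SAP's 68% intervals are two-sided: 0.994 × √(2/30) = 0.257, which matches its stated half-width of .26. The same convention is used below.

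**2. What meeting the expectation shows.** With zero events the exact (Clopper-Pearson) two-sided upper limit is 1 − (α/2)^(1/n). With one event it is the p that solves P(X ≤ 1 | n, p) = α/2.

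| Observed | 95% upper limit | 68% upper limit |
|---|---|---|
| 0/150 | 1 − 0.025^(1/150) = 2.43% | 1 − 0.16^(1/150) = 1.21% |
| 1/150 | 3.66% | 2.18% |
| 0/75 (alcohol arm) | 4.80% | 2.41% |
| 0/38 (alcohol-negative mood cell) | 9.25% | 4.71% |

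Every limit is above 1%, at both levels. Excluding 1% with zero events would need ln(0.025)/ln(0.99) = 367.04, so 368 subjects, at two-sided 95%, and ln(0.16)/ln(0.99) = 182.3, so 183, at two-sided 68%.

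**3. A uniform risk.** If the true risk is 1% in every cell, P(X ≤ 1 | 150, 0.01) = 0.56. At 2% it is 0.20.

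**4. Masking of a concentrated risk.** Let the alcohol-negative mood cell (38) have risk p and the other 112 have risk q. The expectation is met with probability P(0 in cell) × P(≤ 1 elsewhere) + P(1 in cell) × P(0 elsewhere).

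For p = 3% and q = 0: 0.97^38 + 38 × 0.03 × 0.97^37 = 0.314 + 0.369 = 0.68.

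For p = 3% and q = 1%: P(0 elsewhere) = 0.99^112 = 0.324 and P(≤ 1 elsewhere) = 0.692, so 0.314 × 0.692 + 0.369 × 0.324 = 0.34.

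| Assumed pattern | Risk 3% | Risk 5% |
|---|---|---|
| Alcohol-negative mood cell only, zero elsewhere | 0.68 | 0.43 |
| That cell, 0.5% elsewhere | 0.49 | 0.29 |
| That cell, 1% elsewhere | 0.34 | 0.19 |
| Whole alcohol arm (75), zero in placebo | 0.34 | 0.11 |

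At a 10% risk in the cell the probability is 0.10 with zero elsewhere and 0.04 with 1% elsewhere.

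**5. The denominator.** One affected person among the 150 and one among the 10 gives 2/160 = 1.25%, above the expectation. Leaving out the 10 gives 0.67%, below it.

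**The case against.** The strongest reply is that the SAP states an expectation within a descriptive summary. It does not claim to exclude a 1% risk, no go/no-go rule depends on the figure, and an observed 0/150 or 1/150 does agree with it. That stands. A reader might infer that Hypothesis 1a is a safety criterion the trial is bound to pass; the documents do not support this. What remains is what the reported figure can be taken to mean, and whether it is shown for the groups most exposed.

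The masking figures also depend on assumption. The highest, 0.68 and 0.43, put zero risk on everyone outside one cell, including the others who drink alcohol. If the risk belongs to the whole alcohol arm, or if there is 1% elsewhere, the expectation would more often be missed than met. That stands too, so the range should be quoted, not its upper end.

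Two stronger readings of the pre-pilot are tempting. One is that the 10 are the first to receive alcohol with this induction, and that their events go uncounted. Their beverage is not stated, and nothing says their events go unrecorded; their absence from the percentage is an inference from the word pilot. The other is that the pre-pilot review ignores tolerability, because the SAP there discusses only induction and deception ("We will use these results to adjust the protocol in order to improve success of our mood manipulation and deception"). The Protocol describes a safety interview, a repeat suicidal-ideation screen and follow-up wellness calls for participants, and it refers to a Protection of Human Subjects attachment that is not among the documents. Whether pre-pilot tolerability is reviewed cannot be judged.

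Finally, the SAP removes induction failures and aware participants only from its initial analyses, and Hypothesis 1a must keep the failures in order to count them. They are probably in the adverse-event denominator already. Saying so is a clarification, not the correction of a shown error.

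**Conclusion.** The point holds as a minor improvement to reporting. The planned summary is one pooled percentage with no interval and no breakdown by randomised condition. Meeting it leaves an overall risk of up to 2.4% (no events) or 3.7% (one event) compatible with the data at 95%, and 1.2% or 2.2% at the SAP's own two-sided 68%. With no events at all, the limits are 4.8% in the alcohol arm and 9.3% in the alcohol-negative mood cell.

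These limits rest only on the stated sample sizes and near-equal cells. The chance that a 3% to 5% risk goes unnoticed rests on assumed risks: between 0.68 and 0.19 if it sits in the alcohol-negative mood cell with 0% to 1% elsewhere, and 0.34 to 0.11 if it applies to the whole alcohol arm with none in placebo. The documents do not show that such a risk exists or that masking is likely. They show that the planned summary could not reveal it.

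**What to change.** In the SAP, Hypothesis 1a:

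- Count participants with at least one adverse event, among all who receive a study beverage, regardless of mood-induction or deception failure.
- Show the 10 pre-pilot subjects separately and in the total.
- Report the counts by beverage and by the four cells, with exact 95% intervals.
- Describe the rate below 1% as an expectation that the sample cannot confirm, and state instead the upper limit the data exclude. With no events among the 150 these are about 2.4% overall, 4.8% in the alcohol arm and 9.3% in the alcohol-negative mood cell.

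The cost is a few sentences and one table, built from the adverse-event counts already planned and the randomised assignment. No participants or procedures are added. The downside is that the stated safety figure becomes less favourable, and the cell-level intervals will be wide.

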Pre-Manipulation Mood and Cognition (PANAS-X; Brief Hopelessness Measure)
Manipulation Procedures and Checks
Alcohol or placebo administration; Post drinking BrAC measurement; Manipulation check
Mood induction (positive or negative); Manipulation check: PANAS-X
Outcome Measure: Modified Stroop-Suicide (primary outcome of interest), Brief Hopelessness Measure
Post-Study Procedures: Detoxification (if applicable); Post-Study Verbal Interview, Paykel Suicide Scale
(current; risk screening for post study interview), Debriefing, Payment
Follow up Wollness Check Dhone Calle (day of day following, and wook following)

Follow-up Wellness Check Phone Calls (day of, day following, and week following)

Analytic plan

H1: We will quantify the number of individuals screened and the percentage who are eligible and participate. We will run descriptive statistics to quantify 1) prevalence of successful mood induction, 2) distress ratings post-study session, and 3) number of adverse events. Using measures of effect size, t-tests, and Chi square analyses, we will examine sociodemographic differences in these feasibility factors. H2: We will use measures of effect size, t-tests, and Chi Square analyses to examine sociodemographic differences in suicide-related attentional bias scores. H3: The interactive effect of mood and AUA on suicide-related attentional bias will estimated model be using а general linear of the form $\hat{Y} = \beta_0 + \beta_1 Alcohol + \beta_2 Mood + \beta_3 Alcohol \times Mood$. **H4:** The interactive effect of alcohol expectancies and AUA on suicide-related attentional bias will be estimated using a general linear model of the form $\hat{Y} = \beta_0 + \beta_1 Alcohol + \beta_2 Expectancies + \beta_3 Alcohol \times Expectancies$. For H3 and H4, we will use linear contrasts to estimate effects. Inferences will be conducted using 68% CIs for comparisons of interest, as significance testing is not a primary study aim. See Statistical Design and Power attachment.

Potential Problems, Alternative Strategies, Benchmarks for Success, and Impact

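### Objective 1b applies chi-square and Cramer's V to adverse events expected in at most one of 150 people; listing or an exact test should replace them

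*SAP*

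**What the plan says.** Hypothesis 1a of the SAP (Specific Aim 1) describes three feasibility factors: mood-induction success, expected in at least 75%; distress ratings after the session; and the "number of adverse events (expecting less than 1% of pilot subjects"). Objective 1b then compares sociodemographic groups on all three. It names two effect sizes, Cohen's d and Cramer's V, and then "t-tests and Chi square analyses, we will examine sociodemographic differences (gender, age, race/ethnicity, income, and alcohol use history) in these feasibility factors". Adverse events are not set apart, and no exact test, continuity correction or rule for small counts is given.

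The protocol's Analytic plan says the same under H1: "Using measures of effect size, t-tests, and Chi square analyses, we will examine sociodemographic differences in these feasibility factors".

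The denominator is in the SAP's Power and Sample Size Considerations, which plan for "10 pre-pilot subjects and 150 subjects (approximately 38 per condition combination"). The only subgroup share stated anywhere is in the protocol's Study Participants section: "A sample of 160 community adults (50% female; 10 pre-pilot; 150 pilot, about 38 per condition").

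**The concern.** The plan sends an outcome that it expects to be almost absent through a large-sample test. Pearson's chi-square relies on adequate expected counts in every cell. With zero or one event spread over groups defined by race/ethnicity, income, age or drinking history, the event cells cannot have them.

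The error runs in a definite direction. When the single event happens to fall in a small group, the statistic becomes large. A table by race or income could then show a small p-value and a sizeable Cramer's V that rest on one person. The SAP makes tolerability of the procedures one of the project's goals, so such a table would be read.

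**Working it through.** **Inputs**
- N = 150 pilot subjects (SAP, Power and Sample Size Considerations); the 10 pre-pilot subjects are extra.
- Adverse events in under 1% of pilot subjects (SAP, Hypothesis 1a), read as people with an event.
- Alpha = .05 is assumed. The SAP uses .05 only for the alcohol effects of Hypothesis 3: "at a significance level of .05 the sample size provides 80% power to detect a standardized effect of alcohol intake".
- Uncorrected Pearson is assumed, because the SAP does not say which chi-square statistic it means.
- Subgroup size m is assumed and varied. Only m = 75 (women) follows from the documents.

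The SAP states no precision or power for Objective 1b, so there is no planned figure to reproduce.

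**Step 1: expected events.** 0.01 × 150 = 1.5. Fewer than 1.5 means zero or one person.

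**Step 2: expected count.** With one event and a subgroup of m, the expected event count in that subgroup is m/150. For the smaller of two groups this is at most 75/150 = 0.5.

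**Step 3: test result when the one event falls in the subgroup of m.**
- Pearson X² = N(N − m) / [m(N − 1)]. At m = 31: 150 × 119 / (31 × 149) = 3.86.
- Two-sided Fisher p = m/150 for m below 75.
- Cramer's V = √(X²/150).

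| m | share | X² | Pearson p | Fisher p | V |
|---|---|---|---|---|---|
| 15 | 10% | 9.06 | .003 | .10 | .25 |
| 30 | 20% | 4.03 | .045 | .20 | .16 |
| 31 | 20.7% | 3.86 | .049 | .207 | .16 |
| 32 | 21.3% | 3.71 | .054 | .213 | .16 |
| 45 | 30% | 2.35 | .125 | .30 | .125 |
| 75 | 50% | 1.01 | .32 | 1.0 | .08 |

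The largest subgroup in which one event gives p<.05 is 31 with uncorrected Pearson, 8 with the Yates correction and 7 with Fisher (7/150 = .047).

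**Step 4: more than two categories.** The formula for X² is unchanged, but the degrees of freedom rise. The Pearson limit becomes m = 21 (21/150 = 14%) for three categories and m = 17 (17/150 = 11%) for four.

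**Step 5: false-positive rate.** Given exactly one event and no true difference, the event falls in the small group with probability m/150. At m = 31 that is 20.7%. Without conditioning, at an assumed true event rate of 0.5-1% and summing over all possible event counts, the Pearson rate is:
- m = 10: 4.2-5.8%
- m = 15: 3.8-4.3%
- m = 20: 5.2-5.9%
- m = 25: 6.5-7.3%
- m = 31: 8.3-9.6%

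Over m = 10 to 31, Fisher gives 0.1-1.3%.

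**Step 6: effect size.** With one event, V is determined entirely by the size of the group in which the event falls (.25 at m = 15, .08 at m = 75). It says nothing further about tolerability.

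**Step 7: mood-induction failure.** At 25% failure, the expected number of failures in a group of m is 0.25m, which is below 5 only when m is under 20. Chi-square is otherwise workable for this factor.

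**The case against.** The strongest reply is that nothing here is a decision. Objective 1b has no alpha and no rule that turns a p-value into a conclusion. It puts effect sizes first, and the SAP says that the project's purpose is feasibility and effect-size estimation, not significance testing. Hypothesis 1a handles the adverse-event count itself descriptively. A reader might infer that the plan would declare a minority subgroup less tolerant, or that eligibility for a later study hangs on this table. The documents support neither: a single event gives p<.05 only under the conditions set out above, and no section ties Objective 1b to a later design choice. That part of the reply stands. It does not rescue the method, because the tests are still named and Cramer's V, the effect size meant to replace them, is just as uninformative with one event.

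A second reply is that the 20.7% rate describes one event and nearly the worst subgroup size. This is also right. At true rates of 0.5% and 1%, the chance of no event at all is 0.995^150 = 47% and 0.99^150 = 22%, and the unconditional rate for subgroups of 10 to 20 is close to nominal. The 20.7% should not be read as the error rate of the planned analysis.

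A third reply is that the SAP allows methods robust to distributional assumptions. That sentence, in Statistical Design, follows a histogram check of continuous variables and names nothing for sparse tables. The qualifier that allows tests to be used only where suitable belongs to Hypothesis 2 and is absent from Objective 1b.

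**Conclusion.** The point holds in a limited form. For adverse events, the named chi-square test is invalid at the event rate that the plan itself expects, and Cramer's V is uninformative. This conclusion needs only the stated 1% and 150.

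The size of the consequence rests on assumptions: uncorrected Pearson, alpha .05, and a two-category subgroup of 31 or fewer (14% or 11% of the sample for three or four categories). Whether such a subgroup will exist is not documented. Gender, the only documented split, would not give a small p-value.

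A reader might extend the criticism to all the feasibility factors. The figures do not support that: for mood-induction failure the difficulty is confined to groups under 20. This is a minor correction to an exploratory analysis and does not touch the main hypotheses.

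**What to change.** Amend Objective 1b in the SAP, and the matching H1 sentence in the protocol's Analytic plan, in two respects:
- List each adverse event with the participant's characteristics, and give event proportions with exact confidence intervals. Make no subgroup tests and report no Cramer's V when there are only a few events; state in advance what counts as a few.
- For any other categorical feasibility factor, replace chi-square with Fisher's exact test (Fisher-Freeman-Halton for larger tables) whenever an expected count is below 5.

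The cost is a sentence or two of SAP wording. Exact tests are slightly conservative, which matters little for an exploratory comparison.
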